6.1.5 Treatment duration

Patients will continue to be treated until they are no longer benefiting from s.a. oral panobinostat, develop unacceptable toxicities, withdraw consent, are non-compliant with the protocol, the investigator feels it is no longer in the patient's best interest to continue panobinostat therapy (e.g. disease progression, pregnancy, etc.) or the patient dies, whichever comes first. A patient will reach the end of the roll-over study when panobinostat is permanently discontinued. A 30-day safety follow-up should be conducted after the last dose of panobinostat. At every quarterly visit, the investigator is required to confirm that the patient continues to have clinical benefit and may continue receiving study treatment.

The study is expected to remain open for 5 years or until such time that enrolled patients no longer need treatment with s.a. oral panobinostat, whichever occurs first. The study can be terminated at any time for any reason by Novartis.

6.1.6 Starting dose rationale

The starting dose of panobinostat should be the same as the last dose that was given in the parent study. After this, the dose of panobinostat is based on the investigator's judgment.

6.2 Dose modifications

For patients who do not tolerate the specified dose, dose adjustments are permitted in order to allow the patient to continue treatment. The following guidelines should be applied.

If a patient requires a dose delay more than 28 days from the intended day of the next scheduled dose, the patient should be considered for discontinuation of treatment. If, however, the patient was clearly benefitting from treatment and the cause of the delay has resolved, the patient may be able to restart treatment after discussion with Novartis. This option should be used with the highest amount of caution keeping the safety of the patient in mind, and evaluating whether or not the benefit outweighs the risk.

6.2.1 Non-Cardiac Toxicity Dose Modifications

Treatment dose and/or schedule modification may be required based on individual tolerability. Clinical judgment on how to continue the treatment should be exercised when a patient experiences adverse drug reactions.

If a dose reduction is required, the dose of panobinostat should be reduced by decrements of 5 mg (i.e. from 20 to 15 mg or from 15 to 10 mg). The dose should not be reduced below 10 mg daily and the same treatment schedule should be maintained.

6.2.2 Thrombocytopenia

If patients experience thrombocytopenia (TCP), panobinostat may need to be temporarily withheld and the subsequent dose may need to be reduced. In patients with Common Terminology Criteria for Adverse Events version 3.0 (CTCAE) grade 3 ($<50 \times 10^9/L$, complicated by bleeding), or grade 4 ($<25 \times 10^9/L$) thrombocytopenia, panobinostat therapy should be withheld and resumed at a reduced dose upon recovery to \leq grade 2 ($\geq 50 \times 10^9/L$).

Discontinuation of treatment may be considered if thrombocytopenia does not improve despite the treatment modifications described above and/or the patient requires repeated platelet transfusions.

Table 6-2 Thrombocytopenia dose modifications

Thrombocytopenia grade on day of treatment	Modification of panobinostat starting dose	Panobinostat dose on recovery to \leq grade 2 thrombocytopenia ($\geq 50 \times 10^9/L$)
Grade 3 with bleeding Platelets $< 50 \times 10^9/L$	Omit dose	Resume at reduced dose
Grade 4 Platelets $< 25 \times 10^9/L$	Omit dose	Resume at reduced dose

6.2.3 Gastrointestinal toxicity

Gastrointestinal toxicity is very common in patients treated with panobinostat. Patients who experience diarrhea and nausea or vomiting may require temporary dose discontinuation or dose reduction.

Table 6-3 Diarrhea dose modifications

Adverse drug reaction	Grade on day of treatment	Modification of panobinostat starting dose	Panobinostat dose on recovery to \leq grade 1
Diarrhoea	Grade 2 despite anti-diarrheal medicinal product	Omit dose	Resume at the same dose
	Grade 3 despite anti-diarrheal medicinal product	Omit dose	Resume at reduced dose
	Grade 4 despite anti-diarrheal medicinal product	Discontinue	Discontinue

At the first sign of abdominal cramping, loose stools, or onset of diarrhea, it is recommended that the patient be treated with anti-diarrheal medication (e.g. loperamide). Prophylactic antiemetics should be administered at the discretion of the physician and in accordance with local medical practice.

6.2.4 Neutropenia

Neutropenia may require temporary or permanent dose reduction.

Table 6-4 Neutropenia dose modifications

Neutropenia grade on day of treatment	Modification of panobinostat starting dose	Panobinostat dose on recovery to grade 2 neutropenia ($< 1.5-1.0 \times 10^9/L$)
Grade 3 neutropenia ($< 1.0-0.5 \times 10^9/L$)	Omit dose	Resume at same dose
Grade 4 neutropenia ($< 0.5 \times 10^9/L$) or febrile neutropenia ($< 1.0 \times 10^9/L$ and fever $\geq 38.5^\circ C$)	Omit dose	Resume at reduced dose

In case of grade 3 or 4 neutropenia, physicians should consider the use of growth factors (e.g. G-CSF) according to local guidelines. Discontinuation of treatment may be considered if neutropenia does not improve despite the dose modifications and/or despite the addition of colony stimulating factor therapy according to local medical practice and treatment guidelines, and/or in case of severe secondary infections.

6.2.5 Follow-up for toxicities

Patients whose treatment is interrupted or permanently discontinued from study treatment due to an AE or abnormal laboratory value should be followed at least once a week during drug hold and be followed for 4 weeks, and subsequently at 4-week intervals, until resolution or stabilization of the event, whichever comes first. All patients will be followed for AEs and SAEs for 30 days following the last dose of panobinostat.

6.2.6 Dose modification of panobinostat for prolonged QTcF interval

All cardiac events should be treated as per the local standard of care and referred to a cardiologist if clinically indicated. The central and/or local readings of ECGs will use the Fridericia correction for QTc interval assessment: QTcF. Any final decisions concerning panobinostat dose modifications or permanently discontinuing the patient from study treatment due to QTcF prolongation will be based on the assessment performed by the Investigator.

In case of average QTcF > 450 ms pre-dose:

- Assess the quality of the ECG recording and the QT value and repeat if needed
- Do not initiate study treatment
- Determine the serum electrolyte levels (in particular hypokalemia, hypomagnesemia). If abnormal, correct abnormalities before initiating study treatment.
- Review concomitant medication use for other causes for QT prolongation, and for drugs with the potential to increase the risk of drug exposure related QT prolongation (e.g concomitant use of strong CYP3A4 inhibitors)
- Within 7 days, repeat triplicate pre-dose ECG if average QTcF > 450 ms, do not initiate study treatment
- If average QTcF \leq 450 ms, initiate study treatment.

In case of average QTcF > 480 ms, (or average QTcF prolongation >60 ms from baseline) any time after first dose of panobinostat until end of panobinostat treatment:

- Assess the quality of the ECG recording and the QT value and repeat if needed.
- Interrupt panobinostat treatment
- Determine the serum electrolyte levels (in particular hypokalemia, hypomagnesemia). If abnormal, correct abnormalities before resuming study drug treatment.
- Review concomitant medication use for other causes of QT prolongation, and for drugs with the potential to increase the risk of drug exposure related QT prolongation.
- Check study drug dosing schedule and treatment compliance
- Consider more frequent ECG monitoring (e.g. approximately every 2-3 hours between 2 hours post treatment and 6 hours post treatment) until average QTcF is \leq 480 ms)

After confirming ECG reading at site, if average QTcF > 480 ms:

- Interrupt panobinostat treatment
- Repeat ECG and confirm ECG diagnosis by a cardiologist
- If average QTcF confirmed > 480 ms:
 - Correct electrolytes, eliminate culprit concomitant treatments, and identify clinical conditions that could potentially prolong the QT
 - Consult with a cardiologist (or qualified specialist)
 - Increase cardiac monitoring as indicated (e.g., perform approximately hourly ECGs at between 2h post dose of 6h post dose on the same day an average QTcF > 480 ms is reported and pre-dose and at 2h post dose and the next dosing days) until the average QTcF returns to ≤ 480 ms
- After resolution within 7 days to ≤ 480 ms, consider re-introducing panobinostat treatment at the same or reduced dose, and increase ECG monitoring (e.g., pre-dose panobinostat and 2h post panobinostat) for the next treatments:
- If average QTcF remains ≤ 480 ms, continue planned ECG monitoring during subsequent panobinostat treatment.
- If average QTcF recurs > 480 ms after re-introduction of panobinostat treatment or remains > 480 ms for more than 7 days prior to re-introduction, discontinue patient from study treatment.
- Please note that for unscheduled ECGs at any time during panobinostat treatment:
- If a single QTcF is > 480 ms, two additional ECGs should be performed. The three ECGs should be separated by 5-10 minutes. The average QTcF of those three ECGs should be calculated and used for determination of panobinostat dose modifications.

6.2.7 Suggested management of selected adverse events

One of the most common adverse events associated with treatment with oral panobinostat is reversible thrombocytopenia; the degree of thrombocytopenia is dose-dependent. Other side effects include fatigue (dose-dependent), nausea, vomiting and diarrhea.

Diarrhea is especially problematic since, when more severe, can affect drug exposure and result in patient discontinuation. Diarrhea can be controlled with the following regimen which includes of the use of loperamide.

- Patient should be instructed to contact physician at the onset of diarrhea
- Patient should be encouraged to maintain adequate oral hydration (at least 240 ml every 2 hours) with the onset of diarrhea.
- The patient should be instructed to have loperamide readily available and to begin treatment for diarrhea at the first episode of poorly formed or loose stools or the earliest onset of bowel movements more frequent than normally expected for the patient.
- Loperamide 4 mg should be taken at the first loose stool or more frequent than usual bowel movements, followed by 2 mg as needed, no more frequently than every 4 hours, not to exceed a total of 16 mg in 24 hours.

- Patients with diarrhea \geq grade 2 despite this loperamide regimen should interrupt treatment with panobinostat as described in [Table 6-3](#).
- If the above regimen is inadequate then additional evaluation and treatment should be pursued as medically indicated.
- Replacement i.v. fluids and electrolytes may be used as appropriate.
- Additional treatment should be provided in accordance with institutional standard of care and/or local guidelines.
- Premedication with loperamide is not recommended.
- The use of drugs with laxative properties should be avoided because of the potential for exacerbation of diarrhea. Patients should be advised to contact their physician to discuss any laxative use.

For orally administered panobinostat, no grade 4 QTc has been reported with “interrupted” dosing schedules. For oral dose of 20 mg or 60 mg given three times weekly, the incidence of grade 3 QTc prolongation ranges from $<1\%$ to 6%. The largest QTc change is seen approximately five days after the drug is given and does not correlate with drug serum levels.

For detailed safety information as well as the list of adverse drug reactions (i.e. those AEs considered causally related to panobinostat), please refer to the latest panobinostat IB.

6.2.8 Follow up on potential drug-induced liver injury (DILI) cases

Patients with transaminase increase combined with TBIL increase may be indicative of potential DILI, and should be considered as clinically important events.

[figure not shown]
The threshold for potential DILI may depend on the patient’s baseline AST/ALT and TBIL value; patients meeting any of the following criteria will require further follow-up as outlined below:

- For patients with normal ALT and AST and TBIL value at baseline: AST or ALT $> 3.0 \times$ ULN combined with TBIL $> 2.0 \times$ ULN
- For patients with elevated AST or ALT or TBIL value at baseline: [AST or ALT $> 2 \times$ baseline AND $> 3.0 \times$ ULN] OR [AST or ALT $> 8.0 \times$ ULN], combined with [TBIL $> 2 \times$ baseline AND $> 2.0 \times$ ULN]

Medical review needs to ensure that liver test elevations are not caused by cholestasis, defined as ALP elevation $> 2.0 \times$ ULN with R value < 2 in patients without bone metastasis, or elevation of ALP liver fraction in patients with bone metastasis.

Note: (The R value is calculated by dividing the ALT by the ALP, using multiples of the ULN for both values. It denotes whether the relative pattern of ALT and/or ALP elevation is due to cholestatic ($R \leq 2$), hepatocellular ($R \geq 5$), or mixed ($R > 2$ and < 5) liver injury).

In the absence of cholestasis, these patients should be immediately discontinued from study drug treatment, and repeat LFT testing as soon as possible, preferably within 48 hours from the awareness of the abnormal results. The evaluation should include laboratory tests, detailed history, physical assessment and the possibility of liver metastasis or new liver lesions, obstructions/compressions, etc.

1. Laboratory tests should include ALT, AST, albumin, creatine kinase, total bilirubin, direct and indirect bilirubin, GGT, prothrombin time (PT)/INR and alkaline phosphatase.
2. A detailed history, including relevant information, such as review of ethanol, concomitant medications, herbal remedies, supplement consumption, history of any pre-existing liver conditions or risk factors, should be collected.
3. Further testing for acute hepatitis A, B, C or E infection and liver imaging (e.g. biliary tract) may be warranted.
4. Obtain PK sample, as close as possible to last dose of study drug, if PK analysis is performed in the study.
5. Additional testing for other hepatotropic viral infection (CMV, EBV or HSV), autoimmune hepatitis or liver biopsy may be considered as clinically indicated or after consultation with specialist/hepatologist.

All cases confirmed on repeat testing meeting the laboratory criteria defined above, with no other alternative cause for LFT abnormalities identified should be considered as “medically significant”, thus, met the definition of SAE ([Section 8.2.1](#)) and reported as SAE using the term “potential drug-induced liver injury”. All events should be followed up with the outcome clearly documented.

6.3 Concomitant medications

All medications and significant non-drug therapies (including physical therapy and blood or platelet transfusions) administered at the time of entry into this rollover protocol through 30 days after the last panobinostat dosing and the reasons for therapy use should be reported in the source documents at the study center. Medications include not only physician prescribed medications, but also all over-the-counter medications, vitamins, herbals and alternative therapies.

The following restrictions apply during the study:

- No other investigational therapy should be given to patients.
- No anticancer agents other than the study medication (panobinostat) should be given to patients during the study. If such agents are required for a patient then the patient must first be withdrawn from the study.

The following recommendations should be followed for the use of medications that may affect or may be affected by panobinostat treatment:

- For patients who require chronic anticoagulant therapy while on panobinostat therapy, low molecular weight heparin (LMWH) should be the preferred anticoagulant medication. In patients for whom low molecular weight heparin use is to be initiated, the degree of thrombocytopenia should be considered, coagulation parameters monitored, and dose of anti-coagulant adjusted accordingly.

- Concomitant use of strong CYP3A4/5 inhibitors (including, but not limited to, ketoconazole, itraconazole, ritonavir, clarithromycin and telithromycin) should be avoided. If medically necessary, close clinical monitoring of signs and symptoms of panobinostat related AEs is recommended when long-term (≥ 1 week) concomitant administration of any strong CYP3A inhibitors occurs, as this may increase the exposure of panobinostat. Co-administration of panobinostat with a moderate or weak CYP3A inhibitor is allowed. Star fruit, pomegranates or pomegranate juice, grapefruit juice that are known to inhibit CYP3A should be avoided during treatment with panobinostat. In patients with hepatic impairment receiving concomitant medicinal products which are strong CYP3A4 inhibitors, treatment with panobinostat should be avoided due to lack of experience and safety data in this patient population.
- In silico data showed that the systemic exposure of panobinostat may be decreased by 70% in the presence of strong CYP3A4 inducers (including, but not limited to, avasimibe, carbamazepine, phenobarbital, phenytoin, rifabutin, rifampin, St. John's wort). Even though no clinical data are available, panobinostat blood concentrations may be reduced by CYP3A4 inducers. Concomitant use of strong CYP3A4 inducers should be avoided.
- Concomitant use of medications which are known sensitive CYP2D6 substrates (including, but not limited to, tamoxifen, propafenone, risperidone, thioridazine) are to be used with caution. Patients should be carefully monitored for potential signs and symptoms of toxicity and may require dose titration or dose reduction of a sensitive CYP2D6 substrate which also has a narrow therapeutic window (e.g., the ratio of toxicity exposure is ≤ 2 -fold higher than the efficacious or therapeutic exposure).
- Granulocyte growth factors (G-CSF) or red blood cell transfusion may be used for severe neutropenia or for severe anemia, respectively, according to institutional guidelines.
- Patients who were receiving recombinant erythropoietin or darbepoetin alfa prior to starting study drug may continue to receive their pre-study doses throughout the trial.
- Palliative radiation therapy may be permitted, but the need for radiation therapy is usually indicative of disease progression.
- Analgesics for tumor-related pain can be maintained during the study. However, an increase in analgesic use for control of tumor-related pain may indicate disease progression. If an increase in analgesic medication from study entry is required during the study, the patient should be evaluated for progression of disease.
- Anti-emetic medications may be used at the discretion of the Investigator, but consider preferentially the use of metoclopramide. Prophylactic anti-emetics except those listed in [Appendix 14.1](#) can be administered at the discretion of the Investigator. Intravenous dolasetron is contraindicated for preventing nausea and vomiting associated with cancer therapy based on FDA drug safety warning (communication dated 17-December-2010).
- Concomitant use of anti-arrhythmic medicines (including, but not limited to, amiodarone, disopyramide, procainamide, quinidine, and sotalol) and other drugs known to prolong the QT interval (including, but not limited to, chloroquine, halofantrine, clarithromycin, methadone, moxifloxacin, bepridil and pimozone) is not recommended.
- DAC inhibitors (including valproic acid) for any clinical indication are to be avoided while on panobinostat treatment.

For additional information regarding these and other medications please refer to [Appendix 14.1](#) and for detailed safety guidance, please refer to the Investigator's Brochure.

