14.1 Concomitant medication

In general, medications listed in [Table 14-1](#) should be avoided and medications listed in [Table 14-2](#) and [Table 14-3](#) are to be used with caution when co-administered with panobinostat. The use of any of the drugs in [Table 14-1](#), [Table 14-2](#) and [Table 14-3](#) in combination with panobinostat must be discussed with the Sponsor.

14.1.1 Medications which are known to prolong the QT interval and/or induce Torsades de pointes ventricular arrhythmia should be avoided

It is of great importance to avoid such drugs listed below in [Table 14-1](#) in combination with panobinostat, especially in the presence of electrolyte abnormalities, notably decreased potassium or magnesium levels commonly associated with diuretic usage.

This is not a comprehensive list of medications which may prolong the QT interval and/or induce Torsades de pointes. This list of medications was developed in collaboration with an external cardiology consultant and represents those medications which are deemed to have an unacceptable risk of co-administration with panobinostat.

The following website may be referenced as a supplemental guide for drugs which have been associated with Torsades de pointes or prolonging the QT interval but at this time lack substantial evidence for causing Torsades de pointes: azcert.org/medical-pros/drug-lists/drug-lists.cfm.(version 3/25/2008).

Medications listed on the website which do not appear in [Table 14-1](#) above may be used with caution at the discretion of the investigator.

Ondansetron (a known CYP2D6 substrate, see [Table 14-3](#)) has prolongation but has not been shown to cause Torsades de pointes. Therefore, ondansetron is not per se prohibited when combined with panobinostat but caution is to be exercised and close monitoring for signs and symptoms of QT prolongation is recommended.

Table 14-1 Medications which are known to prolong the QT interval and/or induce Torsades de Pointes to be avoided

All Class IA antiarrhythmics	Quinidine Procainamide Disopyramide any other class IA antiarrhythmic drug
All Class III antiarrhythmics	Amiodarone Sotalol Dofetilide Ibutilide any other class III antiarrhythmic drug
Macrolide antibiotics*	Erythromycin clarithromycin
Quinolone antibiotics*	Sparfloxacin
Antifungals	pentamidine

Antimalarials	Halofantrine chloroquine
Antihistamines	Astemizole terfenadine
Anti-emetics	Chlorpromazine Domperidone Droperidol dolasetron (intravenous and oral)^

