Antipsychotics	Thioridazine Mesoridazine Chlorpromazine pimozide
Miscellaneous drugs	arsenic trioxide bepriidil domperidone cisapride levomethadyl methadone
* Note: azithromycin, ciprofloxacin, levofloxacin, pefloxacin, ofloxacin, tosufloxacin, difloxacin, temafloxacin, fleroxacin, acrosoxacin, nalidixic acid and enoxacin are allowed.	
^ Intravenous dolasetron is contraindicated for preventing nausea and vomiting associated with chemotherapy based on FDA drug safety communication dated December 17, 2010. Based on this finding, both intravenous and oral dolasetron are prohibited to be taken with panobinostat.	

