14.1.2 Medications which are known strong CYP3A4/5 inhibitors to be avoided

Panobinostat is a substrate of CYP3A4/5 with minor involvement of CYP2D6, and CYP2C19 in *in vitro* evaluation of its metabolism. Thus, a clinical drug-drug interaction study was conducted using ketoconazole, a strong CYP3A inhibitor, in combination with panobinostat in study CLBH589B2110.

Multiple ketoconazole doses at 400 mg increased C_{max} and AUC of panobinostat by 1.6- and 1.8-fold, respectively, but with no change in T_{max} or half-lives in 14 cancers patients. The less than 2-fold increase in panobinostat AUC upon co-administration of a strong CYP3A inhibitor is considered a weak drug inhibition and not clinically relevant, as panobinostat doses at least 2-fold greater than the evaluated 20 mg dose (i.e., 40 mg and 60 mg have been safely administered in patients. Thus, co-administration of panobinostat with a moderate or weak CYP3A inhibitor is allowed. However, clinical monitoring of signs and symptoms of panobinostat treatment related to adverse events is recommended when long-term (≥ 1 week) concomitant administration of any strong CYP3A inhibitors and panobinostat is medically indicated or investigated in a clinical study.

Patients with impaired liver function (as defined by NCI CTEP criteria) ([Synold et al 2007](#)) are recommended not to receive panobinostat concomitantly with strong CYP3A inhibitors because potential interaction has not been established in this population.

[figure not shown]

Table 14-2 Medications which are known strong CYP3A4/5 inhibitors to be used with caution

Macrolide antibiotics*	Telithromycin troleandomycin
Antifungals (azoles)	Ketoconazole Itraconazole Posaconazole voriconazole
Antidepressants	nefazodone
HIV protease inhibitors:	Indinavir Nelfinavir Ritonavir Saquinavir lopinavir
Miscellaneous drugs or products	¹ Star fruit and pomegranate product and juice convaptan

* azithromycin and regular orange juice are allowed.

¹ [Hidaka et al \(2004\)](#).

Although clarithromycin is a known strong CYP3A inhibitor, it is also known to prolong QT intervals which is listed in [Table 14-1](#) and is prohibited to be taken with panobinostat. This drug is thus not listed again in [Table 14-3](#).

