14.1.3 Medications which are known CYP2D6 substrates to be used with caution

Panobinostat was also shown to be a CYP2D6 inhibitor (K_i 0.17 μ M) *in vitro*. Thus, clinical drug-drug interaction study with panobinostat as CYP2D6 inhibitor and dextromethorphan as CYP2D6 substrate was recently conducted in study [[CLBH589B2109](#)].

Multiple panobinostat doses increased C_{max} and AUC of dextromethorphan by a mean of 1.8- and 1.6-fold respectively, but with no change in T_{max} in 17 cancer patients. An approximately 2-fold increase in dextromethorphan AUC upon co-administration with panobinostat indicated that *in vivo* CYP2D6 inhibition of panobinostat is weak.

As the study was conducted using a sensitive CYP2D6 substrate which resulted in a weak inhibition, drugs with a large therapeutic index such as anti-emetics, anti-hypertensives, and anti-depressants are generally safe to be co-administered with panobinostat.

Patients should be carefully monitored for potential signs and symptoms of toxicity and may require dose titration or dose reduction of a sensitive CYP2D6 substrate which also have a narrow therapeutic window (e.g., the ratio of toxicity exposure is \leq 2-fold higher than the efficacious or therapeutic exposure).

Table 14-3 Medications which are known CYP2D6 substrates to be used with caution

Beta blockers	S-metoprolol Propafenone timolol
Antipsychotics	Aripiprazole Haloperidol Risperidone thioridazine
Antidepressants	Amitriptyline Clomipramine Desipramine Imipramine Fluoxetine Paroxetine Venlafaxine duloxetine
Antiarrhythmics	Mexiletine flecainide
Others	Codeine Dextromethorphan Tamoxifen tramadol
Anti-emetics	ondansetron [^]
[^] Intravenous dolasetron is a CYP2D6 substrate and contraindicated for preventing nausea and vomiting associated with chemotherapy based on FDA drug safety communication dated December 17, 2010. Please see Table 14-1 .	

This is not a comprehensive list of CYP2D6 substrates. Additional updated versions of this list, which are meant to be used as a guide, may be found at the following website: medicine.iupui.edu/clinpharm/DDIs/ClinicalTable.asp.

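### Thioridazine is to be avoided in Table 14-1 but usable with caution in Protocol 6.3 and Table 14-3, with no rule on which governs; clarithromycin's status also differs in strength

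*Protocol*

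**What the plan says.** **Thioridazine.** The CYP2D6 bullet in Protocol 6.3 reads "known sensitive CYP2D6 substrates (including, but not limited to, tamoxifen, propafenone, risperidone, thioridazine) are to be used with caution". Table 14-3, the caution list for CYP2D6 substrates, has it in the antipsychotics row: "Aripiprazole Haloperidol Risperidone thioridazine". Table 14-1, whose title says its drugs are to be avoided for QT prolongation or Torsades, also has it in its antipsychotics row: "Thioridazine Mesoridazine Chlorpromazine pimozide". Section 14.1.1 says the Table 14-1 list "represents those medications which are deemed to have an unacceptable risk of co-administration with panobinostat".

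**Clarithromycin.** It is in Table 14-1, and the note under Table 14-2 says it "is prohibited to be taken with panobinostat". The CYP3A4/5 bullet in 6.3 reads "Concomitant use of strong CYP3A4/5 inhibitors (including, but not limited to, ketoconazole, itraconazole, ritonavir, clarithromycin and telithromycin) should be avoided" and continues "If medically necessary, close clinical monitoring of signs and symptoms of panobinostat related AEs is recommended", with that advice tied to long-term use of one week or more. The QT bullet in 6.3 also names clarithromycin, as not recommended.

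**Mexiletine and flecainide.** Table 14-3 lists both for caution in a row labelled antiarrhythmics. The QT bullet in 6.3 makes anti-arrhythmic medicines as a class not recommended.

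**General rules.** Section 14.1 says that in general Table 14-1 drugs are to be avoided and Table 14-2 and 14-3 drugs used with caution, and that use of any of them has to be discussed with the sponsor. Section 6.3 ends by referring the reader to Appendix 14.1.

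**The concern.** Concomitant-medication rules are operative instructions: a site reads them to decide whether a patient may take a drug. An unacceptable risk and use with caution are different answers to that question, and for thioridazine the protocol gives both. A site that looks only at the CYP2D6 bullet, or only at Table 14-3, could accept a co-administration that Table 14-1 is meant to prevent. In the same way, a site that reads only the CYP3A4/5 bullet would not learn that clarithromycin is prohibited.

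The prescribing rule carries weight here because Table 7-1 schedules no ECG and leaves other assessments to local standard of care. Protocol section 12 also permits no authorised deviations and requires significant ones to be reported in the CSR. Whether a given co-administration is a deviation depends on which status holds.

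**Working it through.** There is no planned figure to reproduce. The check sets every status of each drug side by side and then compares the lists.

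| Drug | QT-based status | CYP-based status | Text that reconciles them |
|---|---|---|---|
| Thioridazine | Avoid (Table 14-1); not named in the 6.3 QT bullet | Caution (6.3 and Table 14-3) | None |
| Clarithromycin | Avoid (Table 14-1); prohibited (note under Table 14-2); not recommended (6.3 QT bullet) | Avoid, with a medical-necessity route (6.3) | The note under Table 14-2 lets Table 14-1 govern; 6.3 does not repeat it |
| Mexiletine, flecainide | Not recommended, as anti-arrhythmics (6.3 QT bullet) | Caution (Table 14-3) | None |
| Dolasetron | Prohibited, intravenous and oral (Table 14-1 footnote) | CYP2D6 substrate (Table 14-3 footnote) | That footnote points to Table 14-1 |
| Ondansetron | Not prohibited; caution and monitoring (14.1.1) | Caution (Table 14-3) | 14.1.1 states the status |

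**List comparison.**

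- Table 14-1 has 29 entries. Chlorpromazine and domperidone each appear twice, so 29 − 2 = 27 distinct drugs.
- Overlap with the four drugs named in the 6.3 CYP2D6 bullet: thioridazine.
- Overlap with the five named in the 6.3 CYP3A4/5 bullet: clarithromycin.
- Overlap with Table 14-2: none. Overlap with the 22 drugs of Table 14-3: thioridazine.
- Total: 2 of 27 Table 14-1 drugs also stand in a more permissive CYP list.
- The 6.3 QT bullet names 5 anti-arrhythmics and 7 other drugs, 12 in all. Eleven are in Table 14-1 (all but moxifloxacin, reading the last name as pimozide). Thioridazine is not among the 12.

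**Reasoning.** The opening sentence of 14.1 gives avoidance to one table and caution to another. A drug in both tables therefore receives both statuses from a single sentence. For dolasetron the appendix sees the overlap and resolves it: "Intravenous dolasetron is a CYP2D6 substrate and contraindicated for preventing nausea and vomiting associated with chemotherapy", followed by a reference to Table 14-1. Thioridazine has no such footnote. In 6.3 the only bullet that names it is the permissive one.

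For clarithromycin every text discourages use, and the appendix says which table controls. What remains is strength of wording: prohibited in one place, a conditional route and a recommendation against use in another.

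**The case against.** The strongest reply is that the lists address different mechanisms, QT prolongation and CYP2D6 metabolism. On that view a drug in both is under both rules, and an ordinary reader applies the stricter one. The QT bullet in 6.3 is open-ended and can reach thioridazine. Section 6.3 sends the reader to Appendix 14.1, and the sponsor-discussion rule covers Table 14-3 as well as Table 14-1. For harm to follow, a site would have to read one bullet or table alone and skip the sponsor discussion.

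Much of this stands, and it is why the point is small. It does not settle the status. The QT bullet reaches thioridazine only by inference, and only as not recommended. The appendix to which 6.3 refers contains the same contradiction. The sponsor-discussion rule applies alike to all three tables and sets no order between them.

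A reader might infer that thioridazine is the one drug left without a reconciling note. The documents do not support that, because mexiletine and flecainide also carry two statuses with no note. A reader might also infer that sponsor discussion contradicts the prohibitions on clarithromycin and dolasetron. Section 14.1 opens with a general rule, and the drug-specific prohibitions read naturally as exceptions to it.

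**Conclusion.** The contradiction for thioridazine is real and in current text. The clarithromycin point holds as a difference in strength, and mexiletine and flecainide show a similar tension. Severity is minor. Amendment 01 reports 9 patients enrolled and 3 ongoing, and the documents do not show any patient taking these drugs. SAP 5.4.4 says concomitant therapy is not collected, so no planned analysis changes. The 2-of-27 figure counts list overlap and says nothing about the size of a clinical risk.

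Two stronger readings should be resisted. One is that patients have no QT safeguard because no ECG is scheduled and SAP 5.6 collects none. Section 6.2.6 gives QTcF thresholds, interruption rules, cardiology confirmation and review of concomitant drugs, and ECGs may be done under standard of care. The SAP statement is about data for analysis. The other is that 6.3 permits clarithromycin under adverse-event monitoring alone. The QT bullet and the sponsor-discussion rule apply to it too, and the monitoring advice covers only use of one week or more.

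The conclusion assumes that the supplied text of 6.3 and Appendix 14.1 is complete on these drugs.

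**What to change.** 1. Keep thioridazine in the CYP2D6 bullet of 6.3 and in Table 14-3, so that the interaction information stays, but mark it in both places as *avoid; see Table 14-1*. Name it in the 6.3 QT bullet.
2. In the 6.3 CYP3A4/5 bullet, add *except clarithromycin, which is prohibited; see Appendix 14.1*.
3. Add one sentence to 6.3 and to 14.1: where a drug falls under more than one list or bullet, the strictest status applies. This settles mexiletine and flecainide as not recommended. It should leave room for a note specific to a drug, so that the 14.1.1 text on ondansetron keeps its force.

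The cost is a few lines of wording. Protocol 12.1 requires a written amendment with ethics approval, so the edit can travel with the next one. Design, data collection and analysis stay as they are.
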